#### **VR Mirror Therapy Condition**

Using a VR headset, motion sensors, and VR software, we will create a customized VR treatment for

each participant that engages them in movements and exercises involving their missing limb in a game-like environment. For example, participants may use the headset to engage in activities such as driving a race car around a course requiring both arms, ski down simulated slopes (see illustration), or manipulate objects. We will use a validated “presence” questionnaire to assess realism and level of immersiveness by participants. Preliminary studies of VR among patients with PLP suggest they interpret VR simulations as realistic representations of their body, including physiological responses when engaging the avatar in motion. Compared to standard mirror therapy, the VR adaption to mirror therapy has unique advantages, such as the ability for the avatar to engage in a much broader range of activities and comparatively diminished fatigue compared to usual mirror therapy exercises. The latter advantage may allow VR participants to obtain longer and more frequent mirror therapy treatments that could enhance the intervention. We can also modify the VR environment specifications for participants reporting a history of motion sickness – for example, by decreasing the degree of sensitivity to head movements – to minimize side effects and improve usability.

### Standard Mirror Therapy Condition

Standard mirror therapy makes use of an external mirror, wherein an amputee carries out simple exercises (e.g., clenching & relaxing their fist) with their intact limb while positioned by the mirror in a manner that gives the visual illusion of the missing limb also being engaged in the exercise (see illustration). Users commonly experience changes in PLP and other phantom sensations with mirror therapy. The mirror therapy condition will consist of a 4-week treatment following the same mirror therapy training used in our previous R&D trial that demonstrated significant reductions in PLP severity. Veterans in this treatment will meet with the study coordinator on a weekly basis to receive video-based and didactic education about the theory behind mirror therapy for PLP and instruction with specific mirror therapy exercises to be used in coordination with a study-provided mirror. Participants will spend 10-30 minutes of each visit performing mirror therapy exercises (see Appendix 4 for a description) under supervision and receive instructions to carry out home exercises on a daily basis. They will further complete an at home log of their mirror therapy use during the week that poses the same questions answered by VR participants.

### Year 2 feasibility trial phase (Research Aims 2-3).

In year two of the study, a second sample of PLP patients (N=20) will receive the VR or standard mirror therapy treatment in a feasibility trial. Eligible and consented participants will receive training with the study coordinator and VR development team as part of their baseline visit. The baseline visit will consist of obtaining written informed consent, questionnaires (see below), and training with the VR/mirror therapy equipment. VR participants will be requested to use the VR headset at home daily for at least 30 minutes and no more than 120 minutes, over one or more sessions. We will specifically encourage them to use the VR treatment when experiencing PLP. Mirror therapy participants will receive homework instructions matching the VR recommended practice time and setting. VR training will include how to use the real-time assessment features in the headset. The total baseline visit time is projected to be ~ two hours, and the weekly visits and post-treatment visits ~ one hour (including VR/mirror therapy visit content and questionnaire completion). Participants will receive compensation for time and travel. We will inform VR participants that the headsets can track daily usage time and time of day when used in addition to their self-report feedback, anticipating that this knowledge may encourage adherence. They will have contact information for the VR development team, who will assist with any user problems with the VR equipment during their participation. Mirror therapy participants will similarly receive contact information for the study coordinator for questions. We will request that participants maintain their usual pain medication and psychotropic regimen during the study.

Feasibility outcomes – including satisfaction, adherence, side effects, and mood and PLP changes – will be compared pre-to-post treatment separately for the VR and mirror therapy protocols and between the two treatments. Participants will utilize each treatment for one month. This treatment duration is consistent with periods allowing for pain symptom reductions in previous VR studies and for PLP changes in mirror therapy participants. During this phase, participants will complete in person baseline and weekly visits for four weeks with either the VR technical staff (VR) or study coordinator (mirror therapy) in addition to their daily homework exercise recommendations. Following IMMPACT (Initiative on Methods, Measurement and Pain Assessment in Clinical Trials) guidelines, the baseline and post-treatment visits will include measures of PLP (Phantom Limb Pain Questionnaire (PLPQ), adjustment to amputation and prosthesis (Trinity Amputation

and Prosthetic Experience Scale (TAPES), mood (Beck Depression Inventory), and life quality (Medical Outcomes Study (SF-12). The study coordinator will administer the assessment measures with both treatment groups. Team statistician, [name], will receive outcome data blinded to treatment assignment.

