### Methods

**1. Participants and Enrollment.** In each year of the project, we will recruit samples of Veterans with PLP from primary care and amputee clinics. Co-investigator [name], NP, is the PACT (Primary Aligned Care Team) coordinator in the amputee clinic at the VA San Diego Healthcare System (VASDHS) and has specific recruitment experience with the PLP population from our previous R&D-supported clinical trial for PLP.

**2. Inclusion criteria.** 1) Ages 21-75 Veteran receiving care at VASDHS; 2) Upper or lower extremity amputation with reported PLP for at least six months; 3) PLP intensity  $\geq 4/10$ ; 4) English-speaking, literate, with stable residence; 6) Able to operate a VR headset as evidenced by direct observation. **3. Exclusion Criteria.** 1) Major medical illness that might confound effects of pain on function (e.g., advanced cardiac or pulmonary disease); 2) current active alcohol or substance use disorder as evidenced from medical record; 3) currently active suicidality, homicidality, or unstable psychiatric status in previous three months as measured by direct observation, patient self-report, or medical record; 4) moderate or severe cognitive impairment as demonstrated by medical diagnosis or clinical observation; 5) Prior mirror therapy experience.

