#### *Satisfaction, Feasibility, and Validity Measures*

**1. Client Satisfaction Questionnaire-Revised (CSQ):** measures satisfaction with health care treatment on a four-point Likert scale. **2. Credibility-Expectancy:** Likert-style ratings (0-6) will monitor participant expectations, credibility, and belief in the relevance and usefulness of treatment. **3. Igroup Presence Questionnaire (IPQ):** a measure used to assess immersiveness of VR-type artificial environments that contains subscales assessing three components of presence, spatial presence, involvement, and realness. **4. Side effects:** participants will complete a check list of side effects used by our VR researchers in the prior development testing (e.g., dizziness, headaches, nausea, history of motion sickness).

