Regarding the feasibility trial Aims 2-3, we will assess feasibility of the study and if the use of the VR and mirror therapy treatments are associated with reductions in PLP, mood symptoms, or improvements in function. We will focus on our ability to implement recruitment strategies, conducting this innovative treatment and measurements, recruitment rate, consent rate, reasons for not participating, reasons for dropping off, the rate of missing data, pattern of missing values, adherence rate and subjects satisfaction. Data analyses will proceed in stages. At first, descriptive statistics and exploratory graphing such as frequencies, means, standard deviations, box and whisker plots, stem and leaf diagrams, and scatter plots will be used to assess the distribution and normality of the data in terms of the presence of skew and/or outliers. The continuous outcome data will be transformed if necessary by using an appropriate transformation such as the log transform for skewed long tailed data. Similarly, potential covariates will also be summarized with descriptive statistics and graphs to determine the most appropriate way to treat these variables to determine if a continuous, categorical, or an interval representation is the most appropriate approach. The comparability of the two treatment groups in baseline demographic and clinical features will be tested with analyses of variance (ANOVAs) for continuous variables and Chi-square analyses for dichotomous variables. Our randomization procedure is expected to control patient and treatment variables that might be associated with outcome. Any variables on which the groups differ initially will be explored as covariates in subsequent analyses, and we will take this into account in the interpretation of the outcome. Primary analyses will be based on a hierarchical model (HLM) using an intent-to-treat method that uses all available data. The model will include a random intercept, a random effect for assessment time, and fixed effects for comparison groups and group-by-time interaction. Denominator degrees of freedom will be calculated using the Kenward-Roger small sample correction. Data will be analyzed from all randomized subjects on whom we have a baseline assessment and at least one post-baseline evaluation. All hypothesis tests will be two-sided with alpha set at .05 and a medium to large effect size (i.e., Cohen's  $d \geq 1.0$ ) for changes from baseline to treatment. We will control Type I error by reducing measures to one key variable or a total or composite score when possible and will use Bonferroni correction for secondary outcomes in a domain family and secondary analyses. Using statistical power software for independent sample designs, an  $N$  of 10 for each treatment group and a minimum effect size of 1.0 standard deviation units of PLP (approximately two points on the PLPQ) results in an estimated power of .72 for the within group changes from pre- to post-treatment. The feasibility trial is not powered to detect between group differences. Based on our previous R&D trial, it will require several years of recruitment in a larger study to enable appropriately powered between group comparisons with a PLP sample. However, we will examine group means and standard deviations for the purpose of calculating effect sizes for a future trial application.

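### The plan does not describe asking about falls, collisions or injuries during home headset use, so its side-effect comparison may not be able to speak to them

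*Combined protocol and SAP*

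**What the plan says.** **Who is enrolled.** The inclusion criteria (section B, Methods) admit "Upper or lower extremity amputation with reported PLP for at least six months". The criterion specific to the headset is "Able to operate a VR headset as evidenced by direct observation". No criterion on balance or previous falls is stated.

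**What they do.** Under VR Mirror Therapy Condition, the activities offered as examples include "driving a race car around a course requiring both arms, ski down simulated slopes". The text presents these as things participants may do, customized to the individual. It does not say whether use is seated or standing.

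**Where and for how long.** Under the Year 2 feasibility trial heading: "VR participants will be requested to use the VR headset at home daily for at least 30 minutes and no more than 120 minutes". The same section adds: "Participants will utilize each treatment for one month".

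**What is measured.** The section on satisfaction, feasibility and validity measures describes "a check list of side effects used by our VR researchers in the prior development testing (e.g., dizziness, headaches, nausea", with motion-sickness history as a further example. Table 2 schedules side effects at Baseline, Weeks 2-3 and Week 4. The real-time assessment section adds in-headset visual analogue questions around and during use, which may cover side effects. The Standard Mirror Therapy Condition section gives the mirror arm a home log with the same questions.

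**How the data are used.** The Year 2 section lists side effects among the feasibility outcomes compared before and after treatment and between treatments.

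**The concern.** A fall, a collision with furniture or an injury to the residual limb is an event, not a symptom rating. Both described instruments are illustrated with symptom-type content, and I found no section that mentions recording such events. If the forms match their description, an event would reach the data only if the participant raised it.

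Volunteered reports are also not collected in the same way in each arm. VR participants are given the development team as their contact for equipment problems, while mirror participants are given the study coordinator. Weekly visits are likewise with VR technical staff in one arm and the coordinator in the other. A difference in volunteered events could therefore reflect who was listening.

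The trial is meant to inform whether to invest further and how to design a larger home-use trial. A blank entry for falls could be read there as reassurance, when it would only mean that nobody was asked. Events not asked about at the time cannot be recovered at analysis.

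**Working it through.** The plan states no safety figure, so there is none to reproduce. The check has two parts.

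**1. Each route by which an event could be captured**

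| Route | Where described | Asks about falls or injuries? |
|---|---|---|
| Side-effect checklist | Satisfaction, Feasibility, and Validity Measures; Table 2 | Examples are symptoms and one history item; full form not shown |
| In-headset ratings | Real-Time VR Embedded Pain Assessment | Visual analogue ratings; no event item described |
| Mirror home log | Standard Mirror Therapy Condition | Same questions as VR, so the same gap |
| Contact details | Year 2 section | Unsolicited; different staff by arm |
| Reasons for dropping out | Section C | Only if the event leads to withdrawal |
| Problem reports, open feedback | Table 1; Year 1 procedures | Year 1 only |

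None is described as a prospective event question in Year 2.

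**2. Size**

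Inputs: 10 VR participants (section C: "of 10 for each treatment group and a minimum effect size of 1.0 standard deviation units of PLP"); 30 to 120 minutes a day and one month (Year 2 section). I take one month as 28 days and assume full adherence.

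- Person-days: 10 × 28 = 280.
- Lower bound of use: 280 × 0.5 h = 140 h (14 h per person).
- Upper bound of use: 280 × 2 h = 560 h (56 h per person).

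These totals cover the whole VR arm. The lower-limb share is not given, so hours in that subset cannot be stated.

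If the question is asked of n people and nobody reports an event, the exact two-sided 95% upper limit is 1 − 0.025^(1/n):

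- n = 10: 1 − 0.025^(1/10) = 0.308, or 31%.
- n = 9 (about 10% dropout, as the plan projects): 0.336, or 34%.
- n = 5 (for illustration, if half the arm were lower-limb amputees): 1 − 0.025^(1/5) = 0.522, or 52%.

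The chance that at least one of 10 people has an event is 1 − (1 − p)^10. The documents give no fall rate, so p is assumed:

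| Per-person risk p (assumed) | P(at least one of 10) |
|---|---|
| 5% | 40% |
| 10% | 65% |
| 20% | 89% |

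Ten people cannot establish that the risk is low. They could well produce an event worth knowing about if the risk is moderate, provided someone asks.

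**The case against.** The strongest reply is that the checklist has not been seen. Its examples are introduced as examples, so it may already include a fall or injury item, and event reporting may be set out in consent material outside the text reviewed here. This stands. A reader might infer that falls and injuries are not recorded; the documents support only that recording them is not described.

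A reader might also infer that the checklist is the sole safety instrument. It is not: the headset ratings and the mirror log can cover side effects, and weekly visits, contact numbers and dropout reasons are further routes. But none of these is described as an event question.

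Third, the hazard should not be overdrawn. Skiing is one optional example, posture is not stated, and a two-armed driving game says nothing about balance. Dizziness appears as a checklist example, not as a predicted effect, and the plan cites good short-term tolerability. Nor do the documents establish that headset and mirror differ most in balance-related harm. The point needs none of these readings. It needs only that lower-limb amputees are eligible, that use is at home, and that side effects are compared.

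Finally, with 20 participants the safety estimate will be imprecise whatever is done. True, but that argues for modest conclusions, not against asking.

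**Conclusion.** The point holds in a limited form. As described, the side-effect measures do not ask about falls, near-falls, collisions or injuries. Unless the unseen checklist already does, the between-treatment comparison would rest on symptoms plus volunteered reports and could not inform fall or injury safety for the larger home trial.

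It would be too strong to say that home safety cannot be judged at all, because symptom tolerability is measured. It would also be too strong to treat 140 to 560 hours as exposure of lower-limb amputees: that range is for all 10 VR participants, at full adherence over 28 days, and the fall concern applies mainly to a subset of unknown size.

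This is an inexpensive gap to close in a pilot and does not undermine the trial's other feasibility aims. If the checklist is shown to contain an event item asked alike in both arms, the measurement gap is closed.

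**What to change.** 1. State whether the checklist includes an item on falls or injuries.
2. If it does not, add one yes/no item, with date and short description, to the questionnaire the study coordinator gives at the existing weekly visits. Word it identically in both arms: any fall, near-fall, collision or injury during or shortly after a session since the last visit. The visit questionnaire is the right place, because the headset is described as taking visual analogue ratings confirmed by movement and could not readily hold a dated description.
3. Report the number of persons affected per arm, and by upper- or lower-limb amputation, with exact binomial 95% confidence intervals among those asked. State how many randomized participants were not asked.
4. Give events per hour of use descriptively only, since VR time is logged by the device and mirror time by the participant.

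The cost is one question per visit and one table, with no new staff, visits or procedures. Precision will be poor (0 of 10 still leaves an upper limit of 31%), and the report should say so.

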VR is a novel, technology-based treatment approach that preliminary research has shown to be effective for the management of acute and chronic pain. VR technology is usable by patients in non-clinical environments and includes assessment features that can allow for the real-time collection of data concerning device usage patterns and changes in PLP sensations during daily living circumstances. Several small studies have adapted visual feedback aspects of mirror therapy to VR treatments for PLP. Perry summarized four recent efforts in a 2014 review, with protocols using different motion sensor technology with the patient's intact limb to create an avatar in a simulated VR environment, where the patient engages in different exercises. Patients find these simulations engaging and often effective for PLP. Studies to date adapting visual feedback aspects of mirror therapy to VR, however, are small (5-14 patients), use mostly intermittent practice protocols, did not include Veterans, and employed only passive controls. In the current study, we propose to test a VR for PLP with 20 Veteran amputees using a daily practice protocol, real time assessments to monitor home-based PLP benefits, and will compare to an active control in the form of standard mirror therapy.

The proposed study will take place over a two year period comprised of a 1) a technical innovation and usability phase; and 2) a feasibility trial phase each lasting approximately twelve months.

Table 1. Overview of study proposal: methodology & outcomes.

Study phase	Sample size	Methodology	Primary outcomes
Technical innovation &	N=15	Iterative testing with participants using the VR equipment in order improve usability,	Satisfaction scores, usability ratings, problem reports, side

usability (year 1)		satisfaction, and effectiveness	effects, immersiveness
Feasibility trial (year 2)	N=20	Between groups design comparing VR treatment versus standard mirror therapy to estimate effects for larger scale trial	Adherence, satisfaction, changes in PLP, mood, function, quality of life

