#### **Real-Time VR Embedded Pain Assessment.**

In addition to the development of the VR treatments, a second novel feature of the VR software is the incorporation of real-time PLP assessment and usability information at random intervals prior, during and after VR interaction. The VR assessments will not collect personal health information. Assessment data will be stored in the VR device during usage and connected by study identification number to the participant's database record for download during their in person visits. VR incorporates eye tracking technology that can allow a user to respond to questions about PLP, mood, immersiveness, or side effects using a visual analogue scale presented in the visual field, confirmed by participants' movements (e.g., a nod to confirm or head shake to disconfirm). Incorporation of a real-time pain assessment is merely an extension of the existing participant interaction system used to navigate VR menus, and so is straightforward to create. The ability to incorporate such ratings in the context of the VR protocol provides several compelling advantages over typical paper-and-pencil diary based methods for pain assessment, including 1) increasing validity by eliminating retrospective "backfilling", 2) assuring precise and time stamped collection of pre- and post-session pain intensity, and 3) provision of real-time feedback to participants, which may reinforce participation. Refining the real time assessment features will be part of the Year 1 goals. Dr.'s [name] and [name] each have substantial prior experience with the real-time assessment of psychosocial and behavioral factors.

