### Study Measures

**Table 2. Timetable of Study Measures During Feasibility Trial**

Evaluation/Study Week	Baseline	Weeks 2-3	Week 4
Screening and Qualification	X		
Medical Chart History Review	X		
Dependent Variable Measures			
Phantom Limb Pain Questionnaire (PLPQ)	X	X	X
Trinity Amputation and Prosthetic Experience Scale (TAPES)	X	X	X
Pain Interference (Brief Pain Inventory, SF-12)	X	X	X
Pain Intensity (Numerical Pain Rating Scale)	X	X	X
Mood (BDI)	X	X	X
Treatment Credibility/Feasibility & side effects	X	X	X
Treatment Satisfaction		X	X
Immersiveness of mirror therapy experience		X	X

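### The only stated Year 2 side-effect analysis is a pre-to-post comparison, which can miss side effects that settle before Week 4 or lead to withdrawal

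*Combined protocol and SAP*

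**What the plan says.** **Analysis rule.** The section on the Year 2 feasibility trial phase puts side effects into one sentence with the other feasibility outcomes: "including satisfaction, adherence, side effects, and mood and PLP changes – will be compared pre-to-post treatment", for each arm on its own and between the arms.

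**Collection.** Table 2 has a row "Treatment Credibility/Feasibility & side effects", marked at Baseline, Weeks 2-3 and Week 4. Under Satisfaction, Feasibility, and Validity Measures, "participants will complete a check list of side effects used by our VR researchers in the prior development testing"; the examples are dizziness, headaches, nausea and a history of motion sickness. No recall window, severity grade, or onset or resolution date is given. As to visits, "participants will complete in person baseline and weekly visits for four weeks".

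**Other possible sources.** The section on real-time assessment says that the technology can let a user "respond to questions about PLP, mood, immersiveness, or side effects using a visual analogue scale presented in the visual field". The mirror arm keeps a home log that asks the same questions as the VR arm answers.

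**Outcome lists.** Table 1 gives the Year 2 outcomes as "Adherence, satisfaction, changes in PLP, mood, function, quality of life". Side effects appear in that table for Year 1 only. The feasibility list in section C includes reasons for leaving the study, then "the rate of missing data, pattern of missing values, adherence rate and subjects satisfaction". It does not mention side effects.

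**The concern.** A pre-to-post contrast suits a pain score, where the question is how far the level has moved by the end of treatment. For harms the question is how many people were affected at any time after they started. Dizziness, headache and nausea can come on in early sessions and then settle, or can make a person stop. Comparing a baseline value with an end value can miss the first pattern and has no end value for the second.

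Year 2 asks for 30 to 120 minutes of daily headset use at home for a month. The plan's supporting statement on tolerability (Year 1 procedures) is limited to short-term use, and the Year 1 participants train over two weeks. The Year 2 tolerability result is therefore new information, and section C says that the research is to inform whether more resources should go into VR development. A side-effect rate that depends on who is still attending, and on what is still present at the end, is a weak basis for that decision.

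**Working it through.** The plan states no side-effect rate, so there is no figure to reproduce. The check sets the sections side by side and then illustrates the possible size.

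**Step 1. What the stated rule does with each pattern**

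| Pattern | Pre-to-post comparison as written | Elsewhere in the plan |
|---|---|---|
| Starts early, still present at Week 4 | Captured | – |
| Starts early, settles before Week 4 | Captured only if the Week 4 recall window reaches back far enough | On the Weeks 2-3 checklist, whose use is not stated |
| Person withdraws before a post-treatment checklist | Not included | Under reasons for leaving the study (section C) |

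Section C's analysis set requires a baseline and at least one post-baseline evaluation, so it is wider than Week 4 attenders. It is not stated to govern side effects. Table 2 shows no checklist between Baseline and Weeks 2-3, so a person who leaves in that gap may have no post-baseline checklist at all. The hierarchical model is not stated to apply to side effects either, and a modelled time trend would not give a count of people affected.

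**Step 2. Possible size**

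From the documents: 10 per arm (section C), and dropout of about 10%, or about 1 of 10 per arm (Recruitment Feasibility).

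Assumed, because the documents give no values:
- E, the number ever affected: 3 or 5 of 10
- W, withdrawals because of side effects: 0, 1 or 2
- p, the share of the remaining cases still present at Week 4: 25% to 75%
- a Week 4 checklist that records current symptoms only
- no other missing checklists

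Formulas (expected values):
- Share seen at Week 4 = (E − W) × p / (10 − W)
- Cumulative share = E / 10

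| E | W | p = 25% | p = 75% | Cumulative |
|---|---|---|---|---|
| 3 | 0 | 0.75/10 = 7.5% | 2.25/10 = 22.5% | 30% |
| 3 | 1 | 0.50/9 = 5.6% | 1.50/9 = 16.7% | 30% |
| 3 | 2 | 0.25/8 = 3.1% | 0.75/8 = 9.4% | 30% |
| 5 | 0 | 1.25/10 = 12.5% | 3.75/10 = 37.5% | 50% |
| 5 | 1 | 1.00/9 = 11.1% | 3.00/9 = 33.3% | 50% |
| 5 | 2 | 0.75/8 = 9.4% | 2.25/8 = 28.1% | 50% |

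**Step 3. How much depends on the recall window**

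Suppose instead that the Week 4 checklist covers the whole treatment period. Then p = 1 and the share seen is (E − W) / (10 − W).
- E = 3: 3/10 = 30% with W = 0, 2/9 = 22.2% with W = 1, 1/8 = 12.5% with W = 2.
- E = 5: 5/10 = 50%, 4/9 = 44.4%, 3/8 = 37.5%.

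The gap closes if nobody withdraws and remains if someone does.

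**Step 4. Precision at this sample size**

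Take an assumed case in one arm: 4 of 10 affected, of whom 2 settle, 1 withdraws and 1 persists. With current-symptom recall, Week 4 shows 1/9 = 11% (exact Clopper-Pearson 95% interval 0.3% to 48.2%). The cumulative count is 4/10 = 40% (12.2% to 73.8%). Even 0/10 has an upper limit of 1 − 0.025^(1/10) = 30.8%. The intervals are wide and overlap, so an exact interval belongs beside any reported rate.

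**The case against.** The sentence in the Year 2 section is a loose overview rather than a chosen estimator. It also covers adherence, which has no value before treatment, and satisfaction, which Table 2 does not schedule at baseline. A strict baseline-to-Week-4 contrast is impossible for both. The checklist is completed at Weeks 2-3 as well, reasons for leaving are to be summarised, and side effects are a primary outcome of Year 1 (N=15). On this view the plan is under-specified, and no information is lost.

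Much of this stands. A reader might infer that the plan counts only symptoms still present at Week 4 in people still attending, so that the rate is bound to be understated and VR could be reported as well tolerated when it was not. The documents do not support that. The recall window is not given, and one checklist item is a history, so the list is not purely of current symptoms. With interval recall, or with persistent symptoms, and no withdrawals, the gap can shrink or vanish. The direction of any bias between arms depends on a pattern of effects that nobody yet knows.

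The objection does not remove the point. If the sentence is read loosely, Year 2 side effects have no analysis rule at all, and the remedy is the same.

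A second caution concerns the remedy. Pooling headset answers with the mirror log would not be a fair count. The headset prompts at random intervals, the log is completed by the participant, and the headset side-effect questions are described as possible rather than fixed. A count of people ever affected rises with the number of times they are asked, so pooling could bias the comparison against VR.

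**Conclusion.** The point holds in this form: the one stated side-effect comparison for Year 2 gives no role to the Weeks 2-3 checklists, may miss effects that settle before Week 4, and leaves out people who withdraw before a post-treatment checklist. The reasons for leaving and the section C analysis set offset this only in part. Understatement is possible, not certain. Its size in Steps 2 to 4 rests on assumed numbers affected, persistence and withdrawals, and for effects that settle it also rests on the unstated recall window. The data for a better summary are already scheduled, so this should be settled before the Year 2 data are analysed. It does not call the design of the trial into question.

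**What to change.** 1. Take side effects out of the pre-to-post sentence in the Year 2 section. State instead that, for each arm, the report will give the number and percentage of all participants who started treatment with any new or worsened side effect, relative to the baseline checklist, on any post-baseline visit checklist (Weeks 2-3 and Week 4). Use the same instrument and schedule in both arms, count withdrawals due to side effects as events, and give exact 95% confidence intervals.
2. Show beside it how many participants in each arm had no post-baseline checklist, so that missing data are not read as absence of side effects.
3. State the checklist's recall window so that each checklist covers the interval since the previous one.
4. Report any headset or home-log side-effect answers separately and descriptively, because prompting differs between the arms.
5. Add side effects to the Year 2 outcomes in Table 1 and to the feasibility list in section C.

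The cost is wording in these places, an instruction on the checklist and one extra table. No new visit or instrument is needed. The reported rate may look less favourable, and with 10 per arm its interval will be wide.
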